4.6 Listing

The subjects screened but not randomized/allocated to treatment will be presented with the reason(s) for screen failure in a data listing.

Based on the combined FAS, subject disposition with respect to analysis sets will be listed by site, treatment and subject number, this listing will include information on in which subgroup the subject was allocated to at randomisation. Subjects who discontinued from the trial will be listed by site, treatment, and subject number including information on timing of and reason for discontinuation.

5 Protocol Deviations

Protocol deviations will be rated as either minor or major. Protocol deviations impacting the primary endpoint and thereby affecting the conclusions of the trial will be rated as major. Major protocol deviations will lead to exclusion of data from the per protocol (PP) analysis sets. Data will not be excluded from the data analysis in case of minor protocol deviations.

The list of major protocol deviations includes, but is not restricted to:

- Treatment received not in accordance with randomisation
- Non-compliance with investigational medicinal product (IMP) treatment regimen for >20% of days during the non-menstrual period. The non-menstrual period of each cycle (cycle 1 to 4) is defined as the period from stop date of menstrual bleeding (excluding the stop day) to start of menstrual bleeding (excluding the start date). For a given cycle the stop date is based on the menstrual bleeding pattern form obtained at the beginning of the cycle, and the start date of menstrual bleeding is based on the menstrual bleeding pattern form obtained at the end of the cycle. The calculation of non-compliance percent is based on the combined non-menstrual period for cycle 1 to 4. In case of missing information on start and/or stop dates, the entire cycle in question will be considered as non-menstrual.

Unforeseen deviations deemed to impact the primary endpoint of the trial may additionally be rated as major protocol deviations by the Ferring clinical team, with support from the Syneos team, on the basis of a blinded review of data before declaration of clean-file and lock of database.

The list of major protocol deviations will be detailed and documented in the clean file document prior to database lock.

5.1 Major protocol deviations

Based on the FAS analysis sets major protocol deviations will be summarised (n and %) for each category of protocol deviation, by treatment and in total for each of the three types of lesion (endometrioma, DIE and adenomyosis), for endometriosis (endometrioma and DIE), and for the three types of lesions combined.

5.2 Listing

Based on the combined FAS subjects with minor or major protocol deviations will be listed and the list will be sorted by site, treatment and subject number. The listing will include category and description of protocol deviation. All major protocol deviation will also be listed separately.

6 Analysis Sets

6.1 Full Analysis Sets

For this trial five full analysis sets (FAS) will be defined. One for each of the three types of lesions, one for endometriosis (endometrioma and DIE combined) and one for all three types of lesions combined (referred to as the combined FAS).

For the analysis of endometrioma, the FAS comprises of all randomised and treated subjects with at least one endometrioma lesion ≥ 10 mm at baseline.

For the analysis of DIE, the FAS comprises of all randomised and treated subjects with at least one DIE lesion ≥ 10 mm at baseline.

For the analysis of adenomyosis, the FAS comprises of all randomised and treated subjects with a maximum junctional thickness ≥ 12 mm at baseline or the size of another adenomyosis lesion ≥ 10 mm at baseline.

For the analysis of endometriosis, the FAS comprises of all randomised and treated subjects with at least one endometrioma lesion ≥ 10 mm at baseline and/or at least one DIE lesion ≥ 10 mm at baseline (referred to as the endometriosis FAS).

For the analysis of the three types combined, the FAS comprises of all randomised and treated subjects.

Treatment assignment for summaries and analyses are according to planned treatment. The study was planned to be have a randomisation ratio of 2:1 with 2 subjects receiving quinagolide vaginal ring for each subject receiving placebo vaginal ring, however the randomisation list used during the study had a 1:1 ratio between quinagolide placebo and placebo vaginal ring. The planned treatment used in the FAS is the treatment according to the actually used randomisation list.

6.2 Per Protocol Analysis Sets

For each of the lesion types the corresponding PP analysis set comprises all subjects from the corresponding FAS except those excluded due to major protocol deviations as defined in section 5.

6.3 Safety Analysis Sets

The combined safety analysis set (SAS) comprises all treated subjects and are analysed according to the actual treatment received. If a subject receives both treatments during the trial, quinagolide treatment will be considered as the actual treatment for the safety analysis.

Four additional SAS will be defined. One for each of the three types of lesions, one for endometriosis (endometrioma and DIE).

For the analysis of endometrioma, the SAS comprises of all treated subjects with at least one endometrioma lesion ≥ 10 mm at baseline.

For the analysis of DIE, the SAS comprises of all treated subjects with at least one DIE lesion ≥ 10 mm at baseline.

For the analysis of adenomyosis, the SAS comprises of all treated subjects with a maximum junctional thickness ≥ 12 mm at baseline or the size of another adenomyosis lesion ≥ 10 mm at baseline.

For the analysis of endometriosis, the SAS comprises of all treated subjects with at least one endometrioma lesion ≥ 10 mm at baseline and/or at least one DIE lesion ≥ 10 mm at baseline (referred to as the endometriosis SAS).

7 Trial Population

Unless otherwise specified all tables and listing in this section will be based on the FAS.

All summaries in this section will be performed by treatment and in total for each of the three types of lesion (endometrioma, DIE and adenomyosis), for endometriosis (endometrioma and DIE), and for the three types of lesions combined. In addition, summaries of the three types of lesions combined will be performed by treatment and in total for each site. Listings will be based on the combined FAS only.

Categorical data will be summarised using numbers and percentages in addition to the sum 'all'. The percentages are based on the total number of subjects with a corresponding assessment. Continuous data will be presented, using the number of subjects (n), mean and standard deviation, median, 25th percentile, 75th percentile, minimum and maximum.

7.1 Demographics and Other Baseline Characteristics

7.1.1 Demographics and Body Measurements

Baseline demographics and body measurements (age (calculated using date of visit 1 and time of birth), race and ethnicity, height, weight and BMI) will be summarised.

7.1.2 Vital Signs at Baseline

Baseline vital signs will be summarised as described in section 10.4.

7.1.3 Endometriosis History

Endometriosis initial diagnosis (time since initial diagnosis, method, stage and anatomic location) will be summarised. In case of partial missing date of initial diagnosis, following imputation will be used: If both day and month are missing 01JAN will be used, if only the day is missing 01 will be used as the day.

Endometriosis surgical history since the initial diagnosis (Any history (yes/no), time since, method and type of surgery) will be summarised. In case of partial missing date of initial diagnosis, following imputation will be used: If both day and month are missing 01JAN will be used, if only the day is missing 01 will be used as the day.

Menstrual history and reproductive history will be summarised.

7.1.4 Endometriosis/adenomyosis lesions at baseline

The number of lesions per subject, the size the lesions and the sum of the sizes of the lesion will be summarised.

The occurrence of subjects having more than one lesion type will be summarised for the three types of lesions combined in the following way: The subjects will be categorised in the following groups: Endometrioma lesions only, DIE lesions only, adenomyosis lesions only, endometrioma and DIE lesions, endometrioma and adenomyosis lesions, DIE and adenomyosis lesions, endometrioma, DIE and adenomyosis lesions. This will be based on the occurrence of lesions ≥ 10 mm at the baseline MRI.

7.2 Medical History

Medical history recorded at screening visit will be coded using Medical Dictionary for Regulatory Activities (MedDRA) version 21.0.

Medical history will be summarised by system organ class (SOC) sorted alphabetically and preferred term (PT) sorted in decreasing frequency of occurrence.

Ongoing (ongoing at time of screening) and past medical history will be reported separately and the number of subjects with any ongoing or past medical history will be included.

7.3 Prior and Concomitant Medication

Medications will be coded using the World Health Organization Drug Reference List and will be summarised by ATC classification 1st level (alphabetically), ATC classification 2nd level (in decreasing order of frequency) and treatment group. These medications will be tabulated separately for:

- 1) Prior medication; i.e. medication taken exclusively prior to treatment (i.e. with stop date before date of first ring insertion).
- 2) Concomitant medication, i.e. medication taken during the treatment period (i.e. medication that was not stopped before date of first ring insertion).

The number of subjects with “any medication” will be included in these tables. If the timing of the dose of a concomitant medication cannot be established in relation to the administration of IMP, it will be considered as concomitant medication.

7.4 Physical and Gynaecological Examination

The results of the physical and gynaecological examinations at baseline will be summarised.

7.5 TVU at baseline

Baseline TVU results will be summarised as described in section [9.3.3](#) and [10.6](#).

7.6 Listings

Baseline characteristic not listed elsewhere will be listed sorted by site treatment and subject number.

Medical history will be listed sorted by site treatment subject number, SOC and PT.

All medications will be listed by site treatment, subject number, start date, ATC level 1 and ATC level 2.

8 Exposure and Treatment Compliance

Unless otherwise specified all summaries in this section will be based on the FAS, and will be performed by treatment and in total for each of the three types of lesion (endometrioma, DIE and adenomyosis), for endometriosis (endometrioma and DIE), and for the three types of lesions combined.

Categorical data will be summarised using numbers and percentages in addition to the sum 'all', the percentages are based on the total number of subjects with a corresponding assessment. Continuous data will be presented, using the number of subjects (n), mean and standard deviation, median, 25th percentile, 75th percentile, minimum and maximum.

8.1 Extent of Exposure

Total extent of exposure will be summarised. Total extent of exposure will be based on information from the vaginal ring administration form.

The total extent of exposure will be the date of the last ring removal minus the date of first ring insertion.

Extent of exposure for each cycle (cycle 1 to 4) will also be summarised, but only for the three types of lesions combined. Extent of exposure for each cycle will as above be calculated as the difference in ring removal dates and insertion dates.

Additionally the extent of exposure counted in cycles will be summarised as a categorical variable. A subject is considered exposed in a given cycle if a ring is inserted at visit 2, visit 5, visit 6, or visit 7 respectively.

8.2 Treatment Compliance

The treatment compliance in percent will be summarised. Treatment compliance will be based on information about missed dose from the medication errors form and the vaginal ring administration form.

The compliance percent will be calculated as 100 times the ratio between the number of days exposed to the ring and the expected number of days exposed to the ring.

The expected number of days exposed to the ring is; if the subject completes treatment, the date of visit 8 minus the date of visit 2; and if the subject discontinues treatment the date of withdrawal minus the date of visit 2. The number of days exposed to the ring is based on the vaginal ring administration form and taking information on the number of days with missed dose >24 hours from the medication errors form into account.

Non-compliance with IMP treatment regimen for >20% of days during a non-menstrual period, defined as a major protocol deviation in section 5 will be summarised.

8.3 Listings

Based on the safety analysis set the exposure data from the vaginal ring administration form and the medication errors form will be listed and the list will be sorted by site, treatment, subject number, and date. The listing will include information on, dates of insertion and removals, and type and timing of medication error.

9 Efficacy

9.1 General Considerations

All efficacy endpoints will be summarised using descriptive statistics and will be performed by treatment and in total for each of the three types of lesion (endometrioma, DIE and adenomyosis), for endometriosis (endometrioma and DIE), and for the three types of lesions combined.

Categorical data will be summarised using numbers and percentages (n and % of all observed) in addition to the sum ‘All’, the percentages are based on the total number of subjects with a corresponding assessment in the analysis set. Continuous data will be presented, using the number of subjects (n), mean and standard deviation, median, 25th percentile, 75th percentile, minimum, and maximum, unless otherwise specified.

All statistical tests will be performed using a two-sided test at a 5% significance level. Treatment differences will (where appropriate) be presented with 95% confidence intervals and p-values corresponding to the statistical test of the hypothesis of “equal effect” against the alternative of “different effect”.

9.2 Primary Endpoint

The primary endpoint consists of the following three evaluations, all based on the MRI examinations at baseline and at end-of-treatment:

- The changes from baseline to end-of-treatment in the sum of sizes (mm) of all endometrioma lesions ≥ 10 mm at baseline
- The changes from baseline to end-of-treatment in the sum of sizes (mm) of all DIE lesions ≥ 10 mm at baseline
- The changes from baseline to end-of-treatment in the sum of sizes (mm) of the maximum junctional thickness (if ≥ 12 mm) and all other adenomyosis lesions ≥ 10 mm at baseline

Based on the FAS and the PP analysis sets the absolute sum of sizes at baseline and at end-of-treatment, and the change in the sum of sizes from baseline to end-of-treatment will be summarised. The summaries will be performed by treatment and in total for each of the three types of lesions (endometrioma, DIE, and adenomyosis).

9.2.1 Primary Analyses

The primary analyses are based on the FAS.

For each type of lesion (endometrioma, DIE and adenomyosis), the primary endpoint is the change in the sum of the lesion sizes at end-of-treatment, i.e. the difference between the active treatment

group and the placebo group in the change from baseline in the sum of the lesion sizes of the same type at the end-of-treatment. The baseline is defined as the sum of the sizes of all lesions of the same type ≥ 10 mm obtained from the MRI examination at screening. At end-of-treatment / cycle 4, the sizes of all lesions included at baseline of the same type will be summed. For each type of lesions, subjects with at least one lesion of that type ≥ 10 mm at baseline will be included.

If a subject is prematurely discontinued during or after cycle 2, an end-of-treatment MRI examination will be performed. The results from this end-of-treatment MRI will be used to calculate the primary endpoints.

If the end-of-treatment MRI examination results in an assessment of a lesion size as <5 mm without a precise value (or categorised as detectable), the size of this lesion will be imputed as 2.5 mm. If the end-of-treatment MRI examination results in a lesion assessed as being truly not detectable, the size of this lesion will be imputed as 0 mm.

If the end-of-treatment MRI examination is not performed or is missing, the missing measurement will be imputed using a multiple imputation (MI) strategy. The imputation will be based on a missing at random assumption (MAR). The missing sum of lesion sizes at end-of-treatment will be imputed by regression-based imputation models using treatment group, baseline sum of lesion sizes, and the overall NRS score (at visit 2, 5, 6, 7, 8) as the predictors. The imputation procedure will be repeated 100 times. For technical reasons, the imputation is implemented in two steps as described below.

Firstly any non-monotone missingness of the predictors mentioned above is imputed using the Markov chain Monte Carlo (MCMC) method, assumptions underlying this partial imputation step are such that subjects with missing data follow the same model as other subjects with the same value of the observed predictors that have complete data, and this is a reasonable assumption for this partial imputation, because subjects tend to miss intermediate visits due to scheduling conflicts or other reasons unrelated to their medical condition under study.

Secondly all monotone missingness is imputed, using a standard MAR based MI approach for monotone missingness, which imputes variables one at a time in the following order: the overall NRS score at visit 2, at visit 5, at visit 6, at visit 7, and at visit 8, and finally the sum of lesion sizes at end-of-treatment.

For each type of lesion and each imputation, the primary endpoint will be analysed using an analysis of covariance (ANCOVA) model, with the change in the sum of lesion sizes from baseline measured at end-of-treatment as the dependent variable, the baseline sum of lesions as covariate, and the treatment group as fixed effect. The treatment difference between active treatment versus placebo will be estimated for each of the three types of lesions.

Finally, the 100 different imputations are combined to an estimate of the treatment difference between active treatment versus placebo and its 95% confidence interval and corresponding p-value using SAS Proc Mianalyze.

In order to control the overall type I error at 5%, the Hochberg procedure is implemented by ranking the 3 p-values in a decreasing order. If the largest p-value is ≤ 0.05 , superiority is established for all 3 types of lesions. If the largest p-value is > 0.05 , but the middle p-value is ≤ 0.025 , superiority is established for the two types of lesions with the smaller p-values. If the largest p-value is > 0.05 and the middle p-value is > 0.025 , but the smallest p-value is ≤ 0.0125 , superiority is established for only the type of the lesion with the smallest p-value. If the largest p-value is > 0.05 , the middle p-value is > 0.025 , and the smallest p-value is > 0.0125 , superiority is not established for any of the 3 types of lesions.

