A lower frequency of gastrointestinal adverse events, i.e. nausea and vomiting, was reported following intravaginal administration of quinagolide 75 µg tablets once daily for 5 days, compared with oral administration (Trial 000076). The most frequently reported adverse events (i.e. reported by more than 1 subject) following intravaginal administration of quinagolide tablets were headache, dizziness and vaginal discharge. Single administration of quinagolide vaginal ring at a target release rate of quinagolide 4.5 µg/day, 9 µg/day and 13.5 µg/day was locally and systemically well tolerated with the most frequently reported adverse events being headache, vaginal discharge and nausea (Trial 000155). The majority of adverse events occurring in all treatment groups including the placebo group started during the first week of treatment and were considered to be of mild or moderate intensity. No inhibition of ovarian function or modification of the menstrual cycle was observed during sequential administration of quinagolide vaginal ring at a target release rate of up to 13.5 µg/day (Trial 000207). In addition, quinagolide had no clinically significant effects on clinical chemistry, haematology or urinalysis parameters, nor on vital signs, electrocardiography recordings, physical or gynaecological examinations in any of the phase 1 trials.

Insertion and/or removal of the vaginal rings may be associated with mild discomfort or spotting, which is expected to be transient. Ring discolouration or breakage at glued junction points could also occur but based on the phase 1 data, there has been no safety concerns associated with these findings. New rings manufactured in a different way (i.e. injection-moulded rings instead of glued rings) will be used in the present trial.

Quinagolide is approved as an oral tablet formulation under tradename NORPROLAC for the treatment of hyperprolactinaemia in Europe and in some other countries. The estimated cumulative exposure of quinagolide until now is more than 280,000 patient years, when administered as an oral tablet in the approved dose range of 25-300 µg or higher. The general safety profile of quinagolide is characterised by adverse events involving the gastrointestinal tract and central nervous system. The most frequent adverse events (all reported as very common, i.e. at a frequency of $\geq 10\%$) in

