6.3.6 End-of-Treatment / Cycle 4 Visit / Visit 8 (RM+7 of Cycle 4)

If subjects attend all scheduled visits and complete the treatment, an end-of-treatment visit (visit 8) will be scheduled on RM+6-10 of cycle 4. If subjects are discontinued from the treatment prematurely, an end-of-treatment visit with the following end-of-treatment assessments should be scheduled within 2 weeks of discontinuation.

The following must take place first for all subjects:

- Ensuring the completion and legibility of NRS by the subject
- Ensuring the completion and legibility of the EHP-30 questionnaire by the subject
- Completing the first part of B&B scale based on the subject's verbal responses
- Urine pregnancy test [*note:* results must be negative]
- Blood collection for central laboratory analysis of:
 - Safety laboratory tests of clinical chemistry and haematology parameters
 - Endocrine parameters (prolactin, TSH and IGF-1)
 - Endometriosis biomarkers (VEGF, PIGF, IL-6, CA125 and sFlt-1)
 - Plasma concentrations of quinagolide and its metabolites

The subject will proceed to the following procedures after the above has been completed:

- Vital signs
- Physical examination
- Gynaecological examination
- Transvaginal ultrasound, preferably performed by the same sonographer as at screening (record the sizes of endometrioma / uterine fibroids, if any)
- Investigator completing the second part of B&B scale based on findings from an examination of pelvic tenderness and induration (see section 7.2.2)
- Removal of the used ring by the subject. Supervision by site staff can be provided if needed
- Drug accountability of the ring
- Inquiring bleeding pattern of the immediate past menstrual period (start / stop dates, amount)
- Recording of use of any concomitant medications including analgesics
- Recording of adverse events
- Completion of end-of-treatment form

Finally, for subjects who complete the treatment and subjects who are prematurely discontinued during or after cycle 2, the following must be performed at the site's affiliated radiology department:

- MRI examination [*note:* performed at or close to this visit when the subject has no bleeding and no ring. Fasting (no food or drink) for 3-4 hours in advance]

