9.1 Determination of Sample Size

The sample size calculation is based on demonstrating superiority of quinagolide vaginal ring compared to placebo vaginal ring on the primary endpoint of changes in the sizes of endometrioma, DIE and adenomyosis lesions summed by type on MRI at cycle 4. An important assumption behind the sample size calculation is an equal magnitude of treatment effect for all three types of lesions. For example, for adenomyosis, by assuming an average baseline lesion size of 18 mm and a standard deviation of 4.5 mm,³⁹ a sample size of 24 randomised subjects (16 on active treatment and 8 on placebo) will have 83% power to detect a treatment effect difference of 6 mm (corresponding to a 33% reduction in lesion size) using a two-sample t-test at a 5% two-sided significance level. A similar assumption, i.e. the ratio between treatment effect and standard deviation is 4 to 3, is made for DIE and endometrioma to conclude 24 subjects to be randomised per sub-group. In total, 72 subjects will be randomised in this trial.

Table 9-1 summarises the required sample size in total for different assumptions of treatment effect difference and power.

Table 9-1 Sample Size by Treatment Effect Difference

Difference in the sum of lesion size reduction between quinagolide vaginal ring group and placebo vaginal ring group		Number of subjects in total ^a	
Absolute difference (mm)	Relative difference ^b (%)	Power 80%	Power 90%
4.5	25	39	51
5.0	28	33	42
5.5	31	27	36
6.0	33	24	30
6.5	36	21	27
7.0	39	18	24
7.5	42	15	21

^a Using a 2:1 randomisation and assuming a standard deviation of 4.5 mm.

^b Assuming an average baseline lesion size of 18 mm.

If the drop-out rate in any of the sub-groups are larger than 10%, the sample size of randomised subjects for that sub-group may be increased to up to 30.

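### Cycle-1 stoppers get no end-of-treatment MRI and are imputed close to their arm's average change; for endometrioma, the ultrasound size due at the same visit is left out of the model

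*SAP*

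**What the plan says.** Protocol 6.3.6 schedules an end-of-treatment visit within two weeks for any premature stop. Its procedures include "Transvaginal ultrasound, preferably performed by the same sonographer as at screening", with endometrioma and fibroid sizes recorded. The MRI is listed separately, "for subjects who complete the treatment and subjects who are prematurely discontinued during or after cycle 2". Footnote e of Table 6-1 and Protocol 7.1.1 agree, so a woman who stops in cycle 1 has no end-of-treatment MRI by design.

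SAP 6.1 keeps her in the analysis. The endometrioma full analysis set needs randomisation, treatment and one endometrioma of at least 10 mm at baseline, and nothing after baseline.

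SAP 9.2.1 uses the early MRI of women who stop in or after cycle 2 as their outcome. Missing lesion sums are imputed 100 times under missing at random, "using treatment group, baseline sum of lesion sizes, and the overall NRS score (at visit 2, 5, 6, 7, 8) as the predictors". The NRS scores are filled in visit order and the lesion sum last. The three resulting ANCOVA p-values go into the Hochberg procedure.

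SAP 9.2.2.2 adds two analyses without imputation and one placebo-based imputation, for each lesion type. SAP 9.3.3 uses the TVU endometrioma sum only for its own secondary endpoint.

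**The concern.** Treatment group is a predictor, while exposure and reason for stopping are not. A woman who wore an active ring for days is therefore expected to receive about the active-arm change, estimated from completers and later stoppers. The pain scores can do little to correct this. She normally has an NRS score only at visit 2 and at her end-of-treatment visit, so the others are themselves imputed.

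For endometrioma she should have one post-baseline measurement of the lesion itself, the TVU size, and the model does not look at it. At stake are the primary endometrioma estimate in all randomised and treated women with a qualifying lesion, and the p-value that enters Hochberg. For DIE and adenomyosis the same imputation applies, but no TVU size exists to improve it.

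**Working it through.** **Inputs.** Protocol 9.1 gives the effect and spread: the plan "will have 83% power to detect a treatment effect difference of 6 mm", "assuming an average baseline lesion size of 18 mm and a standard deviation of 4.5 mm", "using a two-sample t-test at a 5% two-sided significance level", with 16 active and 8 placebo. SAP 3.3 reports that the list actually used was 1:1, hence 12 and 12 in a sub-group of 24. No overall, per-arm or cycle-1 drop-out rate is given; 10% appears only as a trigger for raising the sub-group to 30. The share f of the active arm that stops in cycle 1, the effect s in those women, and the TVU–MRI correlation are assumptions below.

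**Plan's own figure.** Noncentrality = 6 / (4.5 × √(1/16 + 1/8)) = 3.08 on 22 degrees of freedom, so power is 83.7%. This reproduces the stated 83%. All 14 cells of Table 9-1 also reproduce. With 12 and 12, power is 87.7%.

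**Bias of the planned imputation.** If women with an MRI have an effect of 6 mm and active cycle-1 stoppers have s, the effect in all women is 6(1 − f) + fs. The planned imputation centres on about 6, so the excess is f(6 − s). With s = 0:

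| f | True effect, all women (mm) | Planned imputation (mm) | Excess |
|---|---|---|---|
| 5% | 5.7 | 6.0 | 0.3 mm (5%) |
| 10% | 5.4 | 6.0 | 0.6 mm (11%) |
| 20% | 4.8 | 6.0 | 1.2 mm (25%) |
| 30% | 4.2 | 6.0 | 1.8 mm (43%) |

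One woman of 12 is f = 8.3%, an excess of 0.5 mm. If stoppers keep half the effect (s = 3), every excess halves. If f = 0, or the drug has no effect, the excess is zero.

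**What TVU can recover.** With end-of-treatment TVU in the model, the effect credited to a no-effect stopper falls from 6 to about 6(1 − L), where L is the squared within-arm correlation of TVU and MRI change. L = 0.5 gives 3.0 mm, L = 0.8 gives 1.2 mm and L = 0.9 gives 0.6 mm.

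**Simulation.** 1,500 trials per row, 20 imputations, 12 per arm, 2 active stoppers with no effect, residual SD 4.5 mm, one summary NRS score. The placebo-based column uses regression predictions without random draws, a simplification. Mean treatment differences in mm:

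| TVU correlation | NRS correlation | Full data | Planned | Planned + TVU | Placebo-based |
|---|---|---|---|---|---|
| 0.7 | 0 | −5.05 | −6.07 | −5.56 | −5.05 |
| 0.7 | 0.3 | −5.11 | −6.05 | −5.59 | −5.12 |
| 0.9 | 0 | −5.04 | −6.03 | −5.23 | −5.04 |
| 0.9 | 0.3 | −5.00 | −5.89 | −5.18 | −4.99 |

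In the first row TVU cuts the excess from 1.02 to 0.51 mm, about half. In the third it falls from 0.99 to 0.19 mm, about four fifths. Both agree with 1 − L (0.51 and 0.19).

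A separate simulation of the same situation, with a TVU error SD of 3 mm and a weak NRS link, moved the estimate from −5.69 to −5.31 against −5.05 with full data. It kept NRS in the model and showed no loss of precision and no bias under the null.

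**The case against.** The strongest reply is that SAP 9.2.2.2 already deals with this. The placebo-based analysis fits a no-effect stopper directly, covers all three lesion types, and in the table above lies closer to full data than the TVU model does. That stands, and it limits the point. But it is a sensitivity analysis: superiority is declared from the primary p-values, which it cannot change. The two analyses without imputation simply leave these women out.

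A reader might infer that early intolerance falls mainly on the active arm, because Protocol 1.3 says that adverse events mostly "started during the first week of treatment and were considered to be of mild or moderate intensity". The documents do not support that. The sentence reports one completed phase 1 trial and covers every treatment group, placebo included; the same section calls the ring well tolerated. It makes early stops conceivable but shows no excess on active. The bias needs active stoppers with a reduced effect, and placebo stoppers are credited with no drug effect.

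TVU is also imperfect. It is due within two weeks of stopping rather than at cycle 4, Protocol 1.2 calls ultrasound more observer-dependent than MRI, and a woman who skips the visit has none. These points reduce L; they do not make NRS the better predictor of lesion size.

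Finally, neither document states an effect regardless of discontinuation as the target, and Protocol 9.6.1 prespecifies missing at random. The word bias here means bias relative to the average effect in all treated women with the lesion, which is what the full analysis set suggests.

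**Conclusion.** The point stands in a limited form. The primary imputation credits an active-arm cycle-1 stopper with roughly the average change of active women who had an end-of-treatment MRI, and for endometrioma it ignores the only post-baseline lesion measurement she is due to have. With no effect in such women, the overstatement of a 6 mm effect is 0.3 to 0.6 mm for 5 to 10% stopping and about 1.2 mm for 20%. The stopping rate and the absence of effect are assumptions, so the actual size is unknown and may be nil.

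It would be too strong to say that the trial scores intolerance as a full drug effect. The imputation applies to any reason for stopping, in both arms, and later stoppers' MRIs also inform the model. Nor does the mechanism create a false signal when the drug has no effect. It is still worth correcting, because the data are already planned and the change is small.

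**What to change.** Before unblinding, in SAP 9.2.1 and in the matching multiple imputation of SAP 9.2.2.2, add the baseline and end-of-treatment TVU endometrioma sums (already derived for SAP 9.3.3) to the endometrioma imputation model. Impute them before the MRI sum, and keep treatment group in the primary model, the baseline MRI sum and the NRS scores. State also which visit an early stopper's end-of-treatment NRS is stored under, since this decides whether her gap at visits 5 to 7 is treated as intermediate.

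Protocol 9.6.1 allows other measurements in the imputation and leaves the detail to the SAP, so the cost is SAP wording and programming. An extra MRI for cycle-1 stoppers is no longer practicable, because the SAP was written after the last patient's last visit.

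Downsides: the change helps endometrioma only, removes only part of the bias, gives endometrioma a slightly different imputation model from the other two lesion types, and adds two predictors in about 24 women. For DIE and adenomyosis the placebo-based analysis remains the only counterweight and should be reported beside the primary result.
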